1.1.3 Requirements for the proportion of recruited subjects

In order to increase the homogeneity of study subjects, study subjects can be recruited with reference to the following gender and age requirements:

① 20% male, 80% female; ② 30%-35% aged 60-65 years, ③ 30%-35% aged 66-70 years, ④ 30%-35% aged 71-75 years, ⑤ less than 10% aged 76-80 years.

(2) Sample size estimation

After scientific calculations, combined with the actual work, a total of 888 people are needed for this project, then each group needs a sample size of $n=111$, and a total of 37 people are recruited in each street (town). The sample size calculation process is as follows:

This study uses the dichotomous variable "whether a fall occurs" as the outcome indicator. According to the results of the occurrence of falls among the elderly in the community in Guangzhou City in 2023, the incidence of falls among the elderly in Baiyun District was 17%. After discussion with experts, it was concluded that a 35% reduction in the incidence of falls after the intervention was considered to be of public health significance. In this study, the test level was set at $\alpha=0.05$ and the test efficacy at 0.8 (i.e., $\beta=0.2$). The proposed factorial design for this study is based on the sample size formula (below) for factorial designs in which the outcome variable is a dichotomous variable, and the sample size required for each test condition can be obtained as:

$$n = \frac{(Z_{1-\alpha/2} + Z_{1-\beta})^2}{2^k [\arcsin(\sqrt{\frac{\rho+\rho\delta}{2}}) - \arcsin(\sqrt{\frac{\rho-\rho\delta}{2}})]^2} \approx 83$$

$$\rho=0.17, \delta=0.35, Z_{1-\alpha/2}=1.96, Z_{1-\beta}=0.84, k=3.$$

The total sample size required for the 8 test conditions was:

$$N_{\text{conditions}} = 83 \times 8 = 664$$

According to S. Bhasin, T.M et al, the design effect of whole cluster randomisation can be obtained by estimating $ICC = 0.0076$ and mean number of individuals in the cluster $m = 28$:

$$DE = 1 + (m-1) \times ICC = 1 + (28-1) \times 0.0076 = 1.2052$$

The sample size was set to be the same for the eight test conditions, and the total sample size required for the study was:

$$N = N_{\text{conditions}} \times DE \div (1 - 10\%) \approx 888$$

The required sample size for each test condition was then 111 cases;

Each of the 24 streets recruited 37 study participants.

(3) Intervention groups

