2.4 Assessment Tools

Different assessment tools such as observation record sheets, questionnaires, interview outlines, etc. were selected and used according to the different contents and methods of the process assessment, as detailed in Table 5.

Table 5 List of project process evaluation contents, methods and tools

Content	Subject	Method	Tool
1. Completion rate of group activities by study participants	Study subjects in the intervention group	on-site observation	Record of Participation of Research Subjects in the Project Process (Annex 3)
2. Quality of the organisation and implementation of the intervention	Implementation team activities staff	on-site observation	Panel activity site quality assessment form (annex 6)
3. Satisfaction of study participants with group activities	Study subjects in the intervention group	Survey	Project Activity Satisfaction Questionnaire (Elderly) (Annex 7)
4. Household guidance and assistance in environmental rehabilitation	Staff implementing guidance on environmental improvements to households	Summary of work records	Household Environmental Assessment and Improvement Guidance Record Sheet (Annex 8)

(3) Assessment of effects

It is proposed to study the effect of the intervention at 6 and 12 months after the start of the intervention. The assessment of the occurrence of falls will be collected by filling in the monthly fall calendar; the changes in fall efficacy, knowledge, beliefs and

behaviours will be collected through on-site survey and testing.

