3.2.3 Assessment content

The content of the assessment includes: fall-related knowledge, attitude and behaviour, daily life ability and fall efficacy.

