SPSS20.0 was used for statistical processing. Variables such as general demographic characteristics, disease characteristics, previous falls, and level of social support at baseline were compared to see if there were any differences between the different intervention groups, and variables with differences would be corrected in the subsequent analyses. Intent-to-treat (ITT) analysis is proposed to evaluate the intervention in this study. Descriptive analysis: statistical descriptions of primary outcome variables, secondary outcome variables, intervention implementation and other synergistic factors, etc., and independent samples t-tests (continuous variables such as Older Adult Falls Efficacy Scale scores, Quality of Life Scale scores, Older Adults' Falls Knowledge and Belief Behaviour Scale scores, etc.) and chi-square tests (categorical variables such as attitudes towards the intervention strategy, incidence of falls, etc.) to compare the between-groups differences were used.

The study proposes to assess the economic benefits using Incremental Cost-Effectiveness Ratio (ICER), which is the increased cost per unit of effect.

VIII. Safety Guarantee

- (1) When carrying out the various screening, assessment, training, exercise and other activities of the project, the safety and physical health of the research subjects should be ensured as the first principle.
- (2) During the various screening and assessment processes, research subjects should be clearly informed of the testing methods and possible risks. The project may conduct demonstrations and allow research subjects to practise before taking formal measurements. The staff should remind the participants that they should not pursue "good results" in the test.
- (3) In the process of training and exercise, the basic principles are gradual and according to one's ability, and research subjects should not be forced to perform movements that are beyond their ability. All exercises are subject to the subjective feeling of the research subjects themselves, while attention should be paid to correcting the research subjects' sense of "not obeying the old" and stopping dangerous actions in time.

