4.3 Management of lost visitors

In the event of a missed visit, the reasons for the participant's withdrawal from the study will be recorded in detail in the "Record of Participation of Research Subjects in the Project Process" (Attachment 3), and an evaluation of the effectiveness of the project will be carried out as far as possible according to the actual situation.

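### The plan proposes intention-to-treat, but the t-test it names for the scale scores, with no missing-data rule, defaults to completers and leaves earlier scores unused

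*Combined protocol and SAP*

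**What the plan says.** Section VII (2) sets the principle: "Intent-to-treat (ITT) analysis is proposed to evaluate the intervention in this study". The same paragraph then names the between-group tests, and for scale scores it gives "independent samples t-tests (continuous variables such as Older Adult Falls Efficacy Scale scores, Quality of Life Scale scores" and the knowledge and behaviour score. It also says that "variables with differences would be corrected in the subsequent analyses", without naming a model.

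The scales are measured repeatedly. Section VI (3) opens with "It is proposed to study the effect of the intervention at 6 and 12 months after the start of the intervention" and says that changes in efficacy, knowledge, beliefs and "behaviours will be collected through on-site survey and testing". For 6 months (3.2.3): "The content of the assessment includes: fall-related knowledge, attitude and behaviour, daily life ability and fall efficacy". At 12 months (3.3.3) the baseline content is repeated except for the falls part. Each follow-up visit has a 7-day window (3.2.2 and 3.3.2). The baseline survey covers everyone in the eight groups (VI (1) 1.1.2, Table 4).

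On loss, Section III (2) allows 10%: "N = N_{\text{conditions}} \times DE \div (1 - 10\%) \approx 888". Section IX (4) 4.1 counts as lost both people who refuse to go on with the intervention and people who withdraw after an adverse health outcome, other than hospitalisation for unintentional injury. For those lost, 4.3 says that the reason is recorded and "an evaluation of the effectiveness of the project will be carried out as far as possible according to the actual situation". Section VII (1) adds database cleaning with telephone verification. No definition of the ITT set, imputation rule, repeated-measures model or missing-data sensitivity analysis appears anywhere.

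**The concern.** An independent-samples t-test at 12 months can use only people with a 12-month score. With no other rule stated, the comparison is one of completers, and the ITT label is not delivered for these outcomes. Information already collected goes unused: a baseline score for everyone surveyed, and a 6-month score for anyone lost between the two follow-up visits.

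This matters if those who leave differ from those who stay and the pattern of leaving differs by component. Both are possible under the plan's own definition of loss. Withdrawal through ill health plausibly goes with poorer efficacy and quality-of-life scores. Refusing the intervention means little in Group 5, which receives none. If people doing poorly leave more often where a component is delivered, those remaining look better, and an inert component can appear to improve a score.

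**Working it through.** **Inputs from the documents:** 888 people, 24 streets of 37, 10% loss, ICC 0.0076 (Section III (2)); component allocation (Table 1).

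**Assumptions:** no true effect; 6-to-12-month correlation r = 0.6; loss depends on a low 6-month score with logit slope -0.8 per SD; baseline correlations 0.5 with 12 months and 0.6 with 6 months.

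**1. The plan's own figure.** The printed formula has an arcsine difference of 0.3456 - 0.2373 = 0.1083, so n = 2.8² / (8 × 0.1083²) ≈ 83.5 (stated 83). Then 83 × 8 = 664; 664 × 1.2052 = 800.3; 800.3 / 0.9 = 889.2 (stated 888). The figure reproduces as printed. Loss of 10% leaves 888 × 0.9 = 799, about 400 of 444 per factor level, and 89 people without a 12-month score. Since 799 is close to the 800 needed before the allowance, the allowance protects precision. It does nothing about bias.

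**2. How unequal loss could be.** Only Group 5 receives nothing. Suppose loss differs only between receiving something and receiving nothing, is 10% overall, and is zero in Group 5. Each other group then loses 10% × 8/7 = 11.4%. Every 'Yes' level loses 11.4%, and every 'No' level loses (3 × 11.43% + 0) / 4 = 8.6%. This is the widest gap that mechanism gives.

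**3. Completer bias.** If a fraction p is lost and those lost score D SD below those who stay at 6 months, the completers' 12-month mean is too high by p × D × r. The bias in the contrast is r × (p_Yes × D_Yes - p_No × D_No). A logit slope of -0.8 on a standardised score gives D ≈ 0.75, so r × D ≈ 0.45. The SE is √(2 × [1 + (33.3 - 1) × 0.0076] / 399.6) = 0.079 SD. With k = bias/SE, a nominal 5% test with a correct SE rejects with probability Φ(-1.96 + k) + Φ(-1.96 - k). Simulated values come from 4,000 trials per scenario.

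| Loss Yes / No | Score-dependent at | Formula (SD) | Simulated (SD) | Rejection |
|---|---|---|---|---|
| 11.4% / 8.6% | both | 0.45 × 0.0286 = 0.013 | 0.012 | about 5.3% |
| 14% / 6% | both | 0.45 × 0.08 = 0.036 | 0.035 | about 7% |
| 14% / 6% | Yes only | 0.45 × 0.14 = 0.063 | 0.062 | about 12% |
| 10% / 10% | both | 0 | 0.001 | 5% |
| 10% / 10% | Yes only | 0.45 × 0.10 = 0.045 | 0.045 | about 9% |

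Over a wider range (score-dependent in one level only, D from 0.25 to 1.0, r from 0.5 to 0.7) the bias is 0.01-0.07 SD at 10% loss and 0.03-0.14 SD at 20%.

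**4. Precision from the 6-month score.** With n people per level seen at 6 months and n1 at 12, the variance is (1/n1)(1 - r²(n - n1)/n). For n = 444, n1 = 399.6 and r = 0.7, the effective n is 399.6 / (1 - 0.49 × 0.1) = 420. If 50-100% of those lost have a 6-month score and r is 0.5-0.7, effective n is 405-420 instead of 400 (at 20% loss, 365-394 instead of 355). The gain is small, so the argument is about bias.

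**5. What a likelihood model recovers.**
- If all loss falls after 6 months, using the 6-month score brings the simulated bias to within 0.002 SD.
- If all loss falls before 6 months, a model of follow-up scores alone removes none of it.
- Adding baseline leaves a fraction 1 - (0.6 × 0.5)/0.6 = 0.5 of the early-loss bias. Simulated, 0.034 falls to 0.017 and 0.063 to 0.032.
- Baseline also cuts the SE from about 0.078 to 0.063 SD at the assumed 0.5 correlation, if street effects are stable over time.

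**The case against.** **The plan nowhere says that people are dropped.** This is correct. A reader might infer a stated choice to analyse completers, but the documents do not support that. The t-tests sit under descriptive analysis, later adjusted analyses are mentioned, and the textual defect is silence. What stands is that the t-tests are given as the means of comparing groups, no other method is named for these scores, and the default of that test is completers.

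**Refusers will mostly have no 6-month score.** This also stands. Sessions end in week 8 and the home visit is in week 6 (Section V), so refusal to continue falls mainly before month 6. The 6-month score helps only with later losses. For early ones only baseline is held, so a model that omitted baseline would leave their bias untouched.

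**A gap of 14% v 6% has no support in the plan.** Correct: three of the four conditions at every 'No' level still receive another component. The larger gap is an assumption, shown for range.

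**Missing scores will be limited.** Monthly contact (IX (4) 4.2.2) and home visits or calls after a missed evaluation (4.2.3) should reduce missingness. They are not an analysis rule, and neither they nor telephone verification guarantees an on-site score from someone who has refused.

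**These scores do not decide the trial.** A reader might infer that they drive component selection or the cost-utility result. No section says so: the sample-size outcome is whether a fall occurs, and no utility measure is named.

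**Conclusion.** The point holds as a mismatch between the proposed ITT principle and the only named test for the scale scores. Its likely size is modest: about 0.01 SD under the gap derived from the plan's own design, 0.03-0.06 SD under the larger assumed gap. With equal loss the bias is nil only if the loss mechanism is also the same at both levels; equal rates alone do not protect the comparison (0.045 SD when loss is score-dependent at 'Yes' only). All these figures rest on assumed correlations and loss patterns, because the documents give none.

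It would be too strong to say that a mixed model abolishes the bias. It removes only what observed scores explain: in the illustration, all of it for loss after 6 months and about half for loss before. The change is still worth making, because it uses data already planned and settles the method before results are seen. It neither supports nor undermines N = 888, and the falls outcome is not touched.

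**What to change.** In Section VII (2), for each scale score:

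- Replace the visit-by-visit t-tests with one likelihood-based linear mixed model using the baseline, 6- and 12-month scores jointly. Specify a baseline mean common to all groups, component-by-visit terms, a street random effect and unstructured within-person covariance.
- Include every randomised person with any score, and say that this is how ITT is applied to these outcomes.
- Take the 12-month contrast as the result.
- Add one sensitivity analysis shifting the missing 12-month scores downward (towards worse) at the 'Yes' level. The contrast moves by the fraction missing times the shift: at 10% missing, a 0.5 SD shift moves it by 0.10 × 0.5 = 0.05 SD.
- If a t-test is kept, label it a completer analysis.

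The cost is SAP wording and slightly more analysis work, with no new data. The model relies on scores being missing at random given those observed, which the sensitivity analysis checks. The change should be made before group codes are revealed to the analysts.

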All 24 streets within Baiyun District of Guangzhou City were included in the study area. Sampling should take into account the state of socio-economic development, the age of the population, the gender ratio of the neighbourhood committees (villages) as consistent as possible, and the balanced distribution of the sample; taking into account the principle of cost-effectiveness and the feasibility of the sampling scheme. Through centralised open recruitment, household recruitment and other forms of recruitment, followed by face-to-face survey, telephone survey, on-site assessment, etc., eligible elderly people are selected as intervention research subjects and randomly assigned to each intervention group.

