The study subjects were grouped in a completely randomised manner, with a statistician independent of the research team using a computer to generate random numbers, and equal proportions of the study subjects recruited from the 24 streets (towns) were allocated to the 8 experimental condition groups, so that each experimental condition contained all the study subjects from 3 streets (towns). After grouping was completed, a database of basic information about the study participants was created, as shown in Table 1. This study was blinded only to the data collectors and data analysers.

Table 1 Subgroups of the Community Falls Prevention for Older People Pilot Project

groups	Fall Prevention Education Course	Development of personal exercise skills	Environmental assessment
Group 1	Yes	Yes	Yes
Group 2	Yes	Yes	No
Group 3	Yes	No	Yes
Group 4	Yes	No	No
Group 5	No	No	No
Group 6	No	Yes	Yes
Group 7	No	Yes	No
Group 8	No	No	Yes

IV. Intervention Strategies

(1) Strategy 1: Falls prevention education programme

To organise the research subjects in the intervention group to set up a fall prevention health education activity group, in which the project team will disseminate knowledge and concepts of fall prevention through lectures, discussions, questions and answers, and sharing, so as to enhance the knowledge base required by the research subjects to prevent falls and to cultivate the relevant concepts.

(2) Strategy 2: Developing personal exercise skills

Through lectures, demonstrations, on-site exercises and practices, the project team taught the intervention group participants to improve their balance function, lower limb muscle strength, endurance exercise and other fall prevention exercise skills, and to use fall prevention aids through group activities.

(3) Strategy 3: Environmental Assessment

Through the staff's home assessment and guidance, the project team instructed the study participants to assess the risk factors of fall-related home environment and made suggestions for modification.

V. Main intervention activities

(1) Strategy 1: Fall prevention education programme:

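### Streets appear to be the unit of allocation, but the only outcome tests named ignore street, so a nominal 5% two-group test of falls has a true type I error of about 7.4–8.2%

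*Combined protocol and SAP*

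**What the plan says.** **Allocation.** The sections do not agree.

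- Section III (3) says recruits from the 24 streets are divided equally over eight conditions "so that each experimental condition contained all the study subjects from 3 streets (towns").
- Section III (2) follows the same design. It says that "the design effect of whole cluster randomisation can be obtained by estimating" an ICC of 0.0076 and a mean cluster size of 28, and it multiplies the sample by 1.2052.
- Section III (3) nevertheless opens with "The study subjects were grouped in a completely randomised manner", and Section III (1) says that eligible elderly people are selected and "randomly assigned to each intervention group". Both read as individual randomisation.

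**Analysis.** Section VII (2) lists independent-samples t-tests for the scale scores, and "chi-square tests (categorical variables such as attitudes towards the intervention strategy, incidence of falls, etc.) to compare the between-groups differences were used". The sentence carries a descriptive label, but no other between-group outcome test is named. The only adjustment mentioned concerns baseline characteristics: "variables with differences would be corrected in the subsequent analyses". No model is given for it and street is not mentioned. The documents contain no mixed model, GEE, cluster-robust variance or street term.

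**The concern.** The sample size assumes that people in the same street resemble one another, while the analysis treats all 888 as independent. When whole streets are allocated, differences between streets add to the variance of every comparison between conditions. A t-test or chi-square test leaves that variance out, so its standard errors and p-values are too small. The design effect in the sample size does not repair this. It protects the power of an analysis that allows for clustering and does nothing for the error rate of one that does not.

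The trial is meant to decide which of three components to keep for city-wide use. A false positive would commit scarce primary-care resources to a component that does not work. The number of independent units is also small: four conditions of three streets on each side of a factor give 12 v 12 streets, and any two single conditions give 3 v 3.

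**Working it through.** **Inputs from Section III (2):** two-sided alpha 0.05 (1.96), Z for power 0.84, k = 3, fall incidence 0.17, reduction 35%, ICC 0.0076, m = 28, 10% loss, 24 streets of 37. **From Section III (3):** three streets per condition.

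**1. The plan's own figure.** The arcsine formula gives 83.5 per condition (stated as about 83), and 83 × 8 = 664. DE = 1 + 27 × 0.0076 = 1.2052. N = 664 × 1.2052 / 0.9 = 889.2, against the stated 888 = 24 × 37. The figure is reproduced within rounding. The m of 28 matches 664 / 24 = 27.7.

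**2. Which unit do the documents support?** Three streets of 37 make 111, the stated number per condition. Sections V (3) 3.1, VI 2.3.2 and VI 2.3.3 speak of intervention communities, in one place by group number. Teaching is in groups of 12 (Section V, 1.3 and 2.3). Splitting 37 people over eight conditions would leave about 4.6 per condition in a street (37 / 8), too few to form such groups locally. Street allocation is the better reading.

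**3. True type I error of an unadjusted two-group test of falls.** The formula is 2 × [1 − Φ(1.96 / √DE)], with DE = 1 + (m − 1) × 0.0076. The last column is the shortfall in width of any interval built on the same standard errors, 1 − 1/√DE. The plan itself announces no intervals.

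| People per street | DE | True type I error | Interval too narrow by |
|---|---|---|---|
| 28 (plan's figure) | 1.2052 | 7.4% | 8.9% |
| 33.3 (37 less 10%) | 1.2455 | 7.9% | 10.4% |
| 37 (no loss) | 1.2736 | 8.2% | 11.4% |

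**4. Simulation.** Beta-binomial data were generated under the null with incidence 0.17 and ICC 0.0076.

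- 200,000 runs: the chi-square test rejected 7.4–7.5% of the time at m = 28, 7.8–8.0% at m = 33 and 8.2% at m = 37, over 12 v 12 and 3 v 3 streets. With ICC = 0 it rejected 5.0–5.1%, so the excess comes from clustering.
- A separate 40,000 runs: a t-test on street-level summaries rejected 5.0–5.1% for 12 v 12 streets (22 df) and 4.5–4.6% for 3 v 3 (4 df).

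**5. Sensitivity.** A single chi-square test across all eight conditions (7 df) would have a true error of 11.2%, 12.6% or 13.7% at the three design effects. With ICCs that are not in the documents, the two-group figure would be 11.4–13.5% at an assumed 0.02 and 20.1–24.2% at an assumed 0.05 (m = 28 to 37). These last figures are illustrative only.

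**The case against.** There are four serious points on the other side.

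- **The unit of allocation is disputed by the text itself.** If individuals were randomised within streets, this inflation would not arise from allocation and the design effect would not have been needed. That stands as a condition. It does not rescue the plan, because one of the conflicting statements must then be wrong and the sample size rests on the cluster version.
- **The tests are labelled descriptive, and the promised baseline correction implies a later analysis.** A plain t-test or chi-square test cannot correct for covariates, so some further model may be intended. It is not written down, however, and the stated purpose of the tests is to compare groups. On either view the plan lacks a primary analysis that handles street.
- **The only ICC is given in the calculation for the fall outcome.** This limits the figure: 7.4–8.2% applies to falls. The inflation for the t-tested scores cannot be quantified from the documents.
- **The type of comparison is not specified, and 8.2% assumes no loss.** Both are true. With the planned loss the figure is 7.4–7.9% for a two-group test, and a single eight-group test would be worse.

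The excess over 5% is 2.4 to 3.2 percentage points, which is not dramatic. It is still a relative excess of 48–65% on the plan's own inputs, in the only test named for the outcome on which the trial is sized.

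**Conclusion.** The concern holds: the analysis is wrong as written for the design that the sample size assumes. A nominal 5% two-group test of falls has a true type I error of 7.4% to 8.2%. This rests on three conditions: that streets were allocated, which is the better reading of conflicting text; that the unadjusted tests are the final inference, since no other is named; and that the plan's ICC of 0.0076 applies to Baiyun streets. Confidence is high that street is missing from the analysis. The exact size of the inflation depends on the ICC actually observed.

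**What to change.** 1. Reconcile the allocation wording in Section III (1), (2) and (3), and state what was actually randomised.
2. If streets were allocated, replace the unadjusted outcome tests in Section VII (2) with a mixed-effects or GEE model clustered on street, logistic for falls and linear for scores, with a small-sample correction for 24 streets. An analysis of street-level summaries is a simple alternative.
3. Rest inference mainly on the factorial main effects (12 v 12 streets), and treat contrasts between two single conditions (3 v 3) as much less precise.
4. While rewriting the section, it would help to name the baseline covariates in the model and to report the observed ICC.

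**Cost.** This means SAP wording and modest extra analysis, with no change to data or design. Interval widening relative to an unadjusted analysis is √DE × t / 1.96 − 1. At 33.3 and 37 per street it is:

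- main effects: 18.1% and 19.4% (22 df), or 18.8% and 20.1% (20 df);
- main effects with all eight conditions modelled (16 df): 20.7% and 22.1%;
- two single conditions (4 df): 58.1% and 59.9%.

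Part of this is already paid for, because the sample was enlarged by 1.2052, which offsets about 9.8% in interval width (√1.2052 = 1.098).

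### The trial is sized for three component main effects under street-level randomisation, but the analysis section names only tests between groups, with no component contrast and no street term

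*Combined protocol and SAP*

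**What the plan says.** **Aim.** Sections I and II (2) 1.1 set out to screen the individual components and choose the best combination, because the earlier package could not show which component did the work.

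**Sizing.** Section III (2) takes any fall as the outcome and states: "The proposed factorial design for this study is based on the sample size formula (below) for factorial designs". It uses k = 3, two-sided 0.05 and 80% power, and obtains 83 per condition. It then says "the design effect of whole cluster randomisation can be obtained by estimating" an ICC of 0.0076 and 28 people per cluster. With 10% loss this gives 888, or 111 per condition and 37 in each of 24 streets.

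**Allocation.** Section III (3) says "The study subjects were grouped in a completely randomised manner". The same sentence ends by saying that "each experimental condition contained all the study subjects from 3 streets (towns". Table 1 lists Groups 1 to 8 by the presence or absence of each component.

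**Analysis.** Section VII (2) proposes intention-to-treat. It compares the groups at baseline and says that "variables with differences would be corrected in the subsequent analyses". The tests follow under this label: "Descriptive analysis: statistical descriptions of primary outcome variables, secondary outcome variables, intervention implementation and other synergistic factors". They are independent-samples t-tests for scale scores and, for falls, "chi-square tests (categorical variables such as attitudes towards the intervention strategy, incidence of falls, etc.) to compare the between-groups differences were used". The paragraph then turns to the cost-effectiveness ratio. No factorial model, primary comparison, interaction, multiplicity rule or allowance for streets is stated anywhere.

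**The concern.** A factorial trial of this size works only because every participant contributes to every component's contrast. If the data are instead compared condition by condition, each comparison uses a fraction of the sample. An overall test of eight conditions can show that something differs without saying which component is responsible, and that is the question the trial exists to answer.

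The sample size also allows for clustering, while a plain chi-square or t-test does not. If whole streets were allocated, such a test overstates the evidence and makes it more likely that an inert component is recommended for city-wide use. The baseline correction does not help as written: no later analysis is described, and neither named test takes covariates.

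**Working it through.** **Inputs.** From section III (2): fall rate 0.17, relative reduction 0.35, z-values 1.96 and 0.84, k = 3, ICC 0.0076, cluster size 28, 10% loss, 111 per condition, 37 per street. From section III (3): three streets per condition. My assumptions: one active component; 33 analysed per street (37 x 0.9 = 33.3).

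**1. The plan's figure.** The printed formula uses rates (0.17 + 0.0595)/2 = 0.11475 and (0.17 - 0.0595)/2 = 0.05525. The difference in arcsine square roots is d = 0.10831. Then n = 2.8²/(8 x 0.10831²) = 83.5 per condition (stated as about 83). With DE = 1 + 27 x 0.0076 = 1.2052, 664 x 1.2052/0.9 = 889.2, against a stated 888 = 8 x 111. The figure reproduces.

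**2. What it sizes.** The ordinary two-group arcsine formula gives 2.8²/(2 x 0.10831²) = 334.1 per arm, and 334.1/4 = 83.5. The 2^k divisor is therefore exactly a main-effect sizing, four conditions against four.

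**3. Power by contrast, at one fixed n.** Effective n per condition is 111 x 0.9/1.2052 = 82.9.
- Pooled on/off: Φ(d√(8n) - 1.96) = Φ(2.789 - 1.96) = 0.797.
- One pair of conditions: Φ(d√(2n) - 1.96) = Φ(1.395 - 1.96) = 0.286.
- Eight-group chi-square, 7 df: noncentrality 8n(0.0595/2)²/(0.085 x 0.915) = 7.55, power 0.474.

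At 17% v 11.05%, d = 0.08613 and the noncentrality is 4.87.

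| Test | 11.475% v 5.525% | 17% v 11.05% |
|---|---|---|
| Component on/off, pooled | 80% | 60% |
| Eight-group chi-square | 47% | 31% |
| One pair of conditions | 29% | 20% |

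**4. Type I error if streets are ignored.** With 33 per street, DE = 1 + 32 x 0.0076 = 1.2432.
- Per component: 2[1 - Φ(1.96/√1.2432)] = 2[1 - Φ(1.758)] = 0.079.
- Any of three: 1 - (1 - 0.079)³ = 0.22.
- Eight-group chi-square: P(χ² with 7 df > 14.07/1.2432 = 11.32), about 12 to 13%.

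Simulation (40,000 runs, three streets of 33 per condition, beta-binomial, 17% fall rate) agrees: 0.078 per component and 0.217 for any of three. With no clustering the three figures are 5%, 14% and 5%.

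**5. Street-level analysis.** A 2x2x2 ANOVA of the 24 street proportions has 24 - 8 = 16 residual df. In the same simulation it holds about 5% per component and 14% for any of three. Its power is about 73% at the formula's rates and 53% at 17% v 11.05%. It falls short of 80% because 33 per street gives a larger design effect than the assumed 28, and because a t reference on 16 df is wider than the normal.

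**6. Unit of allocation.** 3 x 37 = 111 matches the stated condition size, while 37/8 = 4.625 is not a whole number. The figures fit whole streets.

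**The case against.** The best defence is that a chi-square or two-sample t-test applied to the yes and no columns of Table 1 is a main-effect test, and that the plan, having used a factorial formula, plainly means this. Section VII (2) also commits to intention-to-treat and foresees later adjusted analyses, so some modelling is intended. That is fair as to intent, but the text does not say it. Table 1 and the assessment-subject paragraphs of section VI use groups for the eight conditions; a stray mention of four research groups in section IX (4) 4.4 defines no component contrast. Even the pooled version of these tests would still ignore streets.

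Three stronger readings are tempting and not supported.
- A reader might set the lowest pairwise power beside the highest pooled power and blame the wording for the whole gap. Part of such a gap comes from using different sample sizes; the comparison must be made at one n, as above.
- A reader might blame the analysis section for the 60% at 17% v 11.05%. That lower level arises because the printed formula evaluates other rates. It is a separate sample-size issue.
- A reader might conclude that individuals were randomised within streets, from the phrase about complete randomisation and from section III (1), "eligible elderly people are selected as intervention research subjects and randomly assigned to each intervention group". The whole-cluster design effect, the statement about three streets per condition and the arithmetic make this unlikely. Complete randomisation can simply mean that streets were drawn without stratification. One clarifying sentence is needed.

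**Conclusion.** The point stands and should be settled before group codes are opened. The sizing is algebraically a pooled main-effect sizing under cluster randomisation, and the analysis text provides neither the contrast nor the cluster term. Followed as written, it leads either to a comparison of conditions with 29% to 47% power where 80% was planned, or to a pooled test whose error rate is about 8% per component and 22% overall.

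The power figures assume one active component and 83 effective participants per condition. The error rates assume whole-street allocation, the plan's ICC of 0.0076 and 33 analysed per street; a different ICC would change them. The 14% for any of three components is not caused by clustering: it follows from three tests at 0.05 each and needs only to be stated.

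**What to change.** In section VII (2), name as the primary analysis a 2x2x2 factorial analysis of any fall within 12 months, with all randomised participants in their assigned condition.
- Primary tests: the three component main effects, coded -1/+1, each at two-sided 0.05 as in the sizing. State the familywise error of roughly 14%. Interactions are secondary.
- Account for street, for example by ANOVA of the 24 street fall proportions (16 residual df) or an equivalent mixed model with a small-sample correction.
- Keep eight-group comparisons under the existing descriptive label.
- In section III (3), state that whole streets were randomised. If individuals were in fact randomised within streets, use street as a stratum instead.
- Give the blinded analysts masked component columns. The unrecognisable group codes in section IX (7) 7.2 do not by themselves allow the component contrasts to be formed.

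**Cost.** Wording, one clarified sentence and three masked columns in the database; recruitment and allocation do not change. The downside is candour about power: about 73% at the formula's rates and 53% at 17% v 11.05%, so the plan should not claim 80% for this analysis. Interactions will be weakly tested: power is about 17% at 17% v 11.05% if a component works only when another is absent. A non-significant interaction should not be read as none.
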